Aim 1: Conduct a feasibility and acceptability study of the RELAX approach in migraine and post-traumatic headache (PTH) patients who visit the NYU Department of Neurology General Practice and/or subspecialty groups or the NYU Concussion Center. We will recruit and randomize subjects (N=400) in the FGP Neurology Group including the MS Center and Headache Center and the NYU Concussion Center to receive the RELAX intervention or monitored usual care (MUC). Both groups will be asked to complete daily diaries, and data will also be collected on measures of recruitment, retention, adherence, and satisfaction with the PMR, the clinically important endpoint. With the PMR, we hypothesize that at least 70% of participants will be adherers (e.g., use RELAXaHEAD at least 4 days/week for 12 weeks). We will assess if the daily diary is acceptable by examining whether there is differential attrition with daily diary completion. We hypothesize no difference between the two groups for acceptability of the diary. We will define acceptability as an average score of ≥4 (0-5 Likert scale) on the 9-item acceptability questionnaire. The outcomes for Aim 1 are the feasibility/acceptability outcomes; number of days of diary entered, number of days of pmr, time spent/day on pmr (Please refer to Table 2)

Aim 2: Conduct within group analyses of the RELAX approach vs MUC.

In the migraine patient population, the primary outcome will be migraine quality of life and migraine disability measured by Migraine Quality of Life (MSQ) and the MIDAS. In the migraine-MS population, a primary outcome will also be MS pain related disability as measured by the MOS Pain Effects Scale (PES). ¹⁵ Secondary outcomes include headache frequency and intensity, stress levels, sleep and psychiatric screens (NIH PROMIS depression and anxiety screens). We hypothesize that at 3 months compared with baseline there will be trends in the RELAX arm towards decreased disability (as measured by the Migraine Disability Assessment Scale (MIDAS)) and improvements in MS pain related quality of life in the MS-migraine patient population.

In the PTH patient population, we will examine the secondary outcomes noted above.

Background

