Our initial sample size was justified based on the feasibility outcome of compliance with PMR among patients in the RELAX group. We anticipated an initial compliance rate of at least 75%. The planned sample size also provided adequate power for the primary exploratory outcome (\square MIDAS from baseline to 3 months) and the secondary outcome (number of headaches/30 days). Considering \square MIDAS as the primary outcome can reduce data skewedness and improve study power. Based on the study, the standard deviation (SD) of \square MIDAS ranges from 5 to 7. Using the conservative estimate of SD=7, group sample sizes of 30, with anticipated 25% dropout leading to approximately 23 patients per group, achieve 80% power to detect a clinically significant difference of 5.75 between the groups, assuming a significance level of 0.05 using a two-sided two-sample t-test.

Subsequently, based on later data, we found that only about half of the participants have full follow-through so the 90 (similar to the NIH request) is more adequate for this.

GenderofSubjects

Both genders will be included.

AgeofSubjects

18-80 (18 – 65 in urgent care)

Racialand Ethnic Origin No enrollment restrictions.

Inclusion Criteria [Box1] age 18-80;(18-65 in urgent care)

Meets migraine criteria based on International Classification of Headache Disorders (ICHD) 3 beta (based on questions in REDCap), Migraine Disability Assessment (MIDAS) score >5. 4+ headache days a month.

OR

Meets Chronic PTH criteria based on International Classification of Headache Disorders (ICHD) 3 beta (based on questions in REDCap) and had 4+ headache days a month, is 3-12 months post initial injury.

OR

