Disability is a commonly used outcome in migraine trials evaluating outcomes of acute and preventative interventions, ^{36,37} because it is easy to understand and is meaningful to patients.

TABLE 2: OUTCOME MEASURES: DEFINITIONS AND SCALES

Aim 1: FEASIBILITY AND ACCEPTABILITY OUTCOMES

Feasibility: a) Proportion of patients who enrolled in the study/were recruited for the study, b) Percentage of patients who did PMR ≥4/7 days of the week, c) Number of days spent doing PMR ≥5 minutes/day as determined with the backend analytics in the RELAXaHEAD app, d) Minutes/day spent doing PMR, e) Reasons for non-adherence

Acceptability: a) Satisfaction using Likert scale questions on RELAXaHEAD usability, content, and functionality b) Willingness to repeat a similar treatment intervention in the future (Definitely No/Probably No/Unsure/Probably Yes/ Definitely Yes) c) Attrition

Aim 2: MIGRAINE QUALITY OF LIFE AND MIGRAINE DISABILITY OUTCOMES

Primary Outcome = Functionality: □□MIDAS: difference between scores of MIDAS ^{32,38} at 3 months and baseline. MOS Pain Effects Scale (PES).

Pain: 50% decrease in frequency and/or intensity of HAs (measured by electronic HA diary data).³⁹ Will control for adherence with PMR. (*Frequency*: # of HA days/30 days starting and ending at midnight; *Intensity*:0 (no HA), 1 (mild HA), 2 (moderate HA), 3 (severe HA) recommended by IHS.³⁹

Acute medications used*: As recommended by IHS:# of days/week treated with medications, # of drug administrations/week for medications. Medications included: NSAIDs, acetaminophen, caffeine, aspirin, triptans, barbiturates, opioids, antipsychotics.

Psychiatric Comorbidity, Stress Levels, and Sleep: PROMIS depression and anxiety screens, the Perceived Stress Scale, 42-44 and Sleep Duration and Quality using Likert Scale questions (How would you rate the quality of your sleep/How rested or refreshed did you feel when you woke-up for the day). 45

Adverse Events: *PMR*: Paradoxical anxiety, time burden/inconvenience, and any other adverse events experienced. Recorded in real time in the study diary.³⁹ As recommended by the IHS: Adverse events will be recorded as follows: Event Severity: Mild, Moderate, Severe; Event Seriousness: Serious, Non-Serious, Start and End Time.³⁹

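### Table 2 defines the headache outcome as a 50% responder on frequency and/or intensity, which has several readings and is not the outcome for which the sample-size text claims power

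*Combined protocol and SAP*

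**What the plan says.** The combined protocol and SAP describes the headache outcome in three places.

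- **Table 2, Pain row:** a "50% decrease in frequency and/or intensity of HAs", taken from the electronic diary. Frequency is the number "of HA days/30 days starting and ending at midnight". Intensity is scored "0 (no HA), 1 (mild HA), 2 (moderate HA), 3 (severe HA) recommended by IHS".
- **Study Design, Phase 2 sample-size text:** the planned size is said to give adequate power for the change in MIDAS and for "the secondary outcome (number of headaches/30 days". The figures that follow concern MIDAS only: the groups "achieve 80% power to detect a clinically significant difference of 5.75 between the groups", "assuming a significance level of 0.05 using a two-sided two-sample t-test".
- **Purpose of the Study, Aim 2:** "Secondary outcomes include headache frequency and intensity, stress levels, sleep and psychiatric screens", with no 50% threshold.

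The plan does not say which component makes a responder, how daily intensity becomes one value per patient, or which windows serve as baseline and follow-up. It names no test or model for this outcome.

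**The concern.** The same diary data are described as a count of headaches, as frequency and intensity without a threshold, and as a yes/no responder. The unit also changes, from headaches in the sample-size text to headache days in Table 2.

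Two things are at stake. Responder rates under the different readings can differ several-fold, so a reported rate cannot be interpreted unless the reading was fixed beforehand. And a power claim made for a count does not carry over to a dichotomy of that count, which usually needs more patients.

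**Working it through.** **1. The plan's own figure.** Inputs from the Phase 2 sample-size text: difference 5.75, SD 7, 30 per group, 25% dropout, two-sided 0.05.
- Standardised effect: 5.75/7 = 0.821. Evaluable per group: 30 × 0.75 = 22.5, about 23.
- Normal approximation: Φ(0.821 × √(23/2) − 1.960) = Φ(2.786 − 1.960) = 79.5%. The exact t-test gives 77.8%.
- The stated 80% is reproduced, marginally high for the t-test. It belongs to MIDAS; nothing comparable is given for headaches.
- With Phase 2 at 90 and about half having full follow-through, an equal split leaves 90 × 0.5 / 2 = 22.5 per arm, so 23 remains the relevant size.

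**2. Responder rate by reading.** Assumption: each component has a 20% response, latent bivariate normal with correlation 0.5.
- P(*both*) = 0.087.
- P(*either*) = 0.20 + 0.20 − 0.087 = 0.313.
- Range, for 20–30% on frequency, 10–20% on intensity and correlation 0 to 0.7: *either* 23–44%, *both* 2–14%.
- If the reading were picked after seeing results, the chance of at least one p < 0.05 among the four under no effect is 12–16% (simulated at 23 and 45 per arm).

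**3. The intensity component is itself undefined.** Take 12 headache days in 30 at mean intensity 2, falling to 6 days at mean intensity 2.
- Averaged over all days: 12 × 2/30 = 0.8 falls to 6 × 2/30 = 0.4, a 50% decrease.
- Averaged over headache days only: 2 stays at 2, no decrease.
- On the second summary the value cannot go below 1 while any headache remains, so a patient starting below 2 cannot halve it.

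**4. Power of a frequency responder.** Assumption: the MIDAS standardised effect of 0.821 applies to a normally distributed change in frequency, cut so that controls respond at rate pC. Then pT = 1 − Φ(Φ⁻¹(1 − pC) − 0.821). At 23 per arm:

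| pC | pT | Power, pooled variance | Power, unpooled variance | n per arm for 80% (pooled) |
|---|---|---|---|---|
| 10% | 32.3% | 45.4% | 48.5% | 52 |
| 20% | 49.2% | 55.1% | 59.0% | 41 |
| 30% | 61.7% | 58.2% | 62.3% | 38 |
| 40% | 71.5% | 58.0% | 62.1% | 38 |
| 50% | 79.4% | 55.4% | 59.3% | 41 |

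For pC = 20%, the difference is 0.292. The null SE is √(0.346 × 0.654 × 2/23) = 0.140 and the alternative SE is √((0.160 + 0.250)/23) = 0.134. Power is Φ((0.292 − 1.960 × 0.140)/0.134), which is 55.1% with unrounded SEs. The continuous analysis has 77.8% and needs about 24–25 per arm for 80%.

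**5. Power of the *either* responder.** Simulation of relative change with assumed SD 0.40 (frequency) and 0.35 (intensity), correlation 0.5, 20% control response on each, 23 per arm, 20,000 runs:

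| Shift in frequency | Shift in intensity | Headache days, t-test | *Either* responder |
|---|---|---|---|
| 0.33 | 0 | 78% | 35% |
| 0.33 | 0.29 | 78% | 69% |
| 0.20 | 0.29 | 39% | 53% |
| 0.10 | 0.29 | 13% | 42% |

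The ordering reverses once intensity responds clearly more than frequency.

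**6. What windows the data support.** Methods & Procedures limits requested app use to an initial 60 days and treats the third month as a check on continued use. Payment for Participation pays for diary entry over those 60 days only. Patients are randomised after consent, and baseline data collection and app download follow. No diary period before randomisation is described, and the eligibility criteria give only a threshold of four headache days a month. A 50% decrease therefore has no defined reference value.

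**The case against.** The best defence is that this is a secondary outcome of a feasibility trial whose Aim 2 looks only for trends, that a 50% responder is a legitimate measure, and that the power figures rest on borrowed or assumed inputs. All of that stands. It limits the weight of the point and makes the percentages illustrative. It does not settle which reading applies, and it does not make a power claim for a count cover a responder.

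A reader might infer more than the documents support:

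- **That every responder reading has less power than headache days.** This fails for *either* when intensity responds more than frequency (53% against 39% above). The documents give no effect on either component.
- **That Table 2 replaces the frequency variable.** The same row defines headache days per 30 days, and Aim 2 lists frequency and intensity without a cut-off. The underlying variables are still planned.
- **That the reading will be chosen to suit the results.** Nothing suggests this. The 12–16% shows only what an unfixed definition would allow.
- **That days 61–90 are the natural window and a screening count is available for adjustment.** The third month lies outside the supported and paid diary period, and the documents do not say that the actual number of headache days is recorded at screening.

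**Conclusion.** The point holds in a limited form. The Pain row does not identify one outcome, and its variable differs in type from the one in the sample-size text and in unit as well. Control responder rates of 31% and 9% from the same data illustrate the ambiguity, assuming 20% response per component and correlation 0.5.

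The adequate-power statement cannot be read as covering the responder. If the MIDAS effect of 0.82 is assumed for frequency, power at 23 per arm falls from about 78% to about 45–62% over control rates of 10–50%, the upper figures coming from the unpooled variance. For the frequency responder, the loss follows from dichotomising; its size depends on the borrowed effect. For the *either* responder no direction can be claimed.

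The consequence is for the interpretation of a secondary result. It does not affect the feasibility aim or the MIDAS calculation.

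**What to change.** Before any between-arm analysis:

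1. Make headache days per 30 days the headache outcome, analysed as a count or continuous variable, RELAX versus MUC. Use the same unit in Table 2, Aim 2 and the sample-size text.
2. State a diary window inside the supported 60 days, for example days 31–60. Treat days 61–90 as a secondary persistence analysis that reports diary completeness by arm.
3. Adjust for baseline headache days per month by recording the actual number at the existing baseline REDCap assessment. Because that assessment is described as following randomisation, enter the number before allocation is disclosed. State in advance what is done for participants already enrolled without it.
4. Keep one supportive responder: a decrease of at least 50% in headache days only.
5. Report intensity separately with a stated summary, for example the mean over headache days.
6. Restrict or restate the adequate-power sentence so that it does not cover the responder, or give the headache inputs behind it.

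The cost is a reworded Table 2 row, an edited sample-size sentence and one REDCap field; no visits are added and a responder rate is still reported. There are two drawbacks. A self-reported baseline is less precise than a diary baseline and is measured differently from follow-up. A month-2 window shows the effect during, not after, the 8-week intervention.

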be the same as before but instead of coming for an in-person appointment, subjects will enroll via virtual sessions. Like before, the data is stored and can be viewed by the PI and study team online. In this iteration, subjects may contact the physician/the physician may contact the subject to discuss app data if s/he wants to discuss headache management as part of clinical care. This is intended to take the place of paper diaries which were used during in-office visits.

Phase 2 of the study will be a two-arm randomized controlled trial (RCT) in the outpatient setting at NYULMC to assess feasibility and acceptability of the RELAX approach. The duration of Phase 2 is 3 months. We are beginning the urgent care RCT in May 2019. All patients will complete a migraine disability and migraine quality of life assessment and track their headache frequency and intensity using our RELAXaHEAD app. Data will be collected from the app and adherence will be reinforced with blinded telephone calls. Data collection on these outcomes are important to determine the user burden of data collection. The subjects will only use the application for an initial 60days based on the data we have to date (from Phase 1), and we will see if subjects continue to use the application during the third month.

The physician / NTV will provide the open-enrollment card to potential subjects when they approach them about the study.

Designated study team members will pre-screen patients in Epic as indicated elsewhere in the procedure using the Epic Research Report. They will obtain patient consent for the study. Once consented, patients will be randomized to RELAX or MUC. The study team member will then collect patients' health histories and baseline data in REDCap on an iPad, download the app onto patients' smartphones, and conduct the sessions (see below). Physicians listed as study staff on this protocol may also consent and enroll eligible patients if they note that one of the patients under his/her care is appropriate for the study. There is currently an Android version and an IOS version. In addition, we will use Data Core to locate potentially eligible patients with migraine within the NYU health system at NYU Langone and NYU Brooklyn sites from primary care and the various neurology divisions. These potential patients will be sent a message via MyChart.

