Week 5: pmr at least 3 days a week (optional body scan)

Weeks 6-8: use when it is most helpful (falling asleep, HA coming on, stress)

The study intervention will be 8 weeks in duration but the full study length will be 6 months. There will be a baseline assessment (T0), a f/u call or email at one week (T1), a 30 day phone call or email assessment (T2), a 60 day phone call/email (T3), and a 90 day phone call/email (T4) (to examine persistence of effect after a month). The last follow up will be at 6 months to examine persistence of effect 4 months after the intervention ends. As we learned previously, we are adding the option for email as some subjects prefer email.

The MUC session is where the subjects are explained that in migraine treatment, they may be given medications to take to stop a migraine and medications to prevent a migraine. The mainstay of migraine management is a headache diary where people can track their headache days, headache intensity, medications taken, and any other details they think might be pertinent to share with their medical provider. No written material is provided during this session.

MUC: To match the time spent with the designated study team member, subjects will be given a general education session consisting of basic migraine information, such as evidence-based ways to treat headaches: treat early, limit acute medications < 2–3 days/week, and call the primary care physician (PCP) if abortive medications are used more frequently. They will be shown a website: https://[name].wixsite.com/relaxahead (to be renamed). The study team member will load the app onto the subject's smartphone but the PMR component will be blocked on the version of the app that the MUC subject receives.

All subjects will be asked to track headache frequency, intensity, and acute medication use on app. All subjects will get the post enrollment card after they have been enrolled so that they have some instructions on what to do when they go home.

All subjects will receive written educational material about migraine.³⁰ All subjects will receive follow-up phone calls, texts, and/or SendSafe emails at 1 week of enrollment and 1, 2, 3, and 6 months after study enrollment. (The choice of calls, texts or emails came from prior subjects who participated in IRB approved study focus groups.) The study team has permission from MCIT to send the following text messages (and an emailing indicating such approval is part of the submission process):

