In addition, if any subject contacts us and want to withdraw from the study, we will ask them to complete the MSQv2 and MIDAS before they withdraw. Subjects who withdrew will be contacted via telephone or email at the end of the 6 months study period in order to verify their email address to be used to send the reimbursement gift card for their study participation. An IRB approved telephone voicemail and email script will be used. An attempt will be made to reach the subject via telephone and a voicemail will be left if unanswered. Following this, an email will be sent.

In addition, we will be conducting focus groups of patients who consented for the study to obtain additional feedback regarding the study procedures. Focus groups will range from 3-7 people with a goal of 5 participants per group. Participants will receive invitations to participate in the focus groups over telephone or over email. If they agree to do so, they will sign an informed consent form at the focus group meeting. Participants will be given a \$50 dollars for participating in the group. The focus group duration will be one hour.

Symptoms Diary

On the smartphone application platform developed by IRODY [end user agreement was already signed as part of prior study-see attached] (used by the NYUMC epilepsy group for ongoing IRB approved studies and in another IRB approved headache study), subjects will be trained to keep records of headache occurrence, side effects, compliance and medicine changes on their mobile device. If a subject fails to consistently record their data, they will receive a call from the RV at NYU to ensure compliance with data maintenance. Information prompted by the device will include:

- 1. Headaches (number, intensity, duration, time)
- 2. Abortive and preventive migraine drug treatment

- 3. Concomitant medications
- 4. Episodes of non-compliance
- 5. Changes made to migraine medication treatment plan, if any, and reasons for the change
- 6. Adverse effects, including severity, seriousness, unexpectedness as part of pharmacovigilance
- 7. Mood and anxiety and stress levels, sleep quality and duration
- 8. Healthcare utilization

The symptoms diary may be accessed via the mobile application only.

The study team will not share the symptoms diary information with the subject's treating physician. However, subjects can elect to share their data with their treating physician independently.

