The application produced by the company IRODY has been used by other researchers in the department of neurology at NYUMC. The symptoms diary on the mobile device used by subjects will be secured to comply with data privacy and other regulatory requirements. Data security is maintained by having a secure data protocol, which encrypts the information being sent from the mobile device to the cloud server and vice versa. The server is protected by a firewall. Daily backups will be performed. The app will not hold any personally identifying details and will be linked only to the Subject ID. The app does not collect any personal information from the mobile device. As stated above, the RVs and PI will have access to the symptoms diary data, as well as all subjects' names and phone numbers, in order to contact any participants who forget or are unable to enter their information in a timely manner. The RVs and PI will access the symptoms diary data only for the purpose of ensuring data completion and will not disclose any subjects' PHI.

Risk/Benefit Assessment

Risk

Risks from PMR: There is minimal harm in doing PMR therapy. PMR may cause some pain in previously injured sites. It may also cause some flooding of memories. If this occurs, subjects will be directed to turn their thoughts elsewhere. If this method is ineffective, subjects will be told that they can stop performing the relaxation.

Potential Breaches of Confidentiality: There is a small risk of breach of confidentiality. Protections against this are described.

ProtectionAgainstRisks

As stated above, subjects will be warned of the side effects.

Potential Benefit stothe Subjects

Subjects may benefit by having decreased migraine disability and by having their migraine pain decrease in severity and/or frequency with the PMR.

Investigator's Qualifications & Experience

Please see attached.

Subject Identification, Recruitment and Consent/Assent MethodofSubjectIdentificationandRecruitment

Virtual enrollment Phase 1:

Recruitment will be done via both direct and indirect contact.

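### Adverse events are solicited only through the app diary; no scheduled contact, missed-diary call or withdrawal step is stated to ask about them, so ascertainment is incomplete in subjects who stop using the app

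*Combined protocol and SAP*

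**What the plan says.** AEs are a listed outcome. Table 2 gives their content for PMR and their source as "Paradoxical anxiety, time burden/inconvenience, and any other adverse events experienced. Recorded in real time in the study diary". The Symptoms Diary section includes among the prompted items "Adverse effects, including severity, seriousness, unexpectedness as part of pharmacovigilance" and states that the diary can be reached only through the mobile app. Under Quality Control, safety concerns are to be identified from the diary download.

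On timing, Methods & Procedures says of Phase 2: "The subjects will only use the application for an initial 60days based on the data we have to date". Third-month use is then observed. The same section says: "The study intervention will be 8 weeks in duration but the full study length will be 6 months". Payment for Participation pays for diary entries over the initial 60 days and doubles the daily amount at 80% completion.

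Contacts are planned at 1 week and at 1, 2, 3 and 6 months. The content given for months 1 to 3 is the MSQv2 and MIDAS, to assess benefit. Subjects with 3 days of missing entries are contacted to resume data entry, and calls stress adherence. For those who withdraw, "we will ask them to complete the MSQv2 and MIDAS before they withdraw". The 6-month contact of withdrawn subjects is described only as confirming an email address for the gift card.

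Risk/Benefit Assessment names two possible harms of PMR, pain at old injury sites and flooding of memories. If redirecting attention does not help, "subjects will be told that they can stop performing the relaxation".

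**The concern.** A subject who leaves the app also leaves the only instrument that asks about AEs. The plan expects that some subjects may stop PMR because of discomfort, and the sample size text reports that "we found that only about half of the participants have full follow-through", so incomplete participation is not a marginal matter. If some of those who leave do so because of an event, nothing in the described contacts would reliably bring it out.

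Two things are at stake. The AE summary for RELAX would rest on fewer subjects than were exposed, and possibly on a selected group. Attrition, which Table 2 counts as an acceptability outcome, could not be reliably divided into loss through harm and loss through lack of interest. The weekly text message shows the same gap: it asks about PMR practised outside the app, but not about problems experienced there.

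**Working it through.** **1. Paid diary window.** The stated Phase 2 maximum payment is $225. Inputs from Payment for Participation: $25 initial survey; $1 per day for 60 days, doubled; $15 at each of 1 and 2 months; $25 at each of 3 and 6 months.

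25 + 2 × 60 + 2 × 15 + 2 × 25 = 25 + 120 + 30 + 50 = 225.

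The figure reproduces, so the paid window is 60 days. This is Phase 2 only; the reopened Phase 1 pays for up to 90 days.

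**2. That window against the exposure and follow-up periods in the document.**
- 8-week intervention: 56 days, fully covered by 60.
- 12-week use in the Aim 1 adherence definition: 60/84 = 71%.
- 3-month Phase 2 duration: 60/90 = 67%.
- 6-month study length: about 60/180 = 33%.

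The 8-week and 12-week statements, and the 3-month and 6-month statements, must be reconciled before any single coverage figure can be quoted.

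**3. Does any described step ask about AEs?**
- Diary: yes, in the app only.
- Contacts at 1, 2 and 3 months: MSQv2 and MIDAS. No AE question stated.
- Contacts at 1 week and 6 months: no AE question stated; no questionnaire is tied to either.
- Contact after 3 days without an entry: reminder to enter data.
- Approved text messages: app, adherence and follow-up reminders, and the weekly PMR-time query.
- Withdrawal: MSQv2 and MIDAS.
- End-of-study contact of withdrawn subjects: email check for payment.

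**4. Illustration of the loss of information.** Inputs: 90 Phase 2 subjects; 1:1 allocation (an assumption, as the ratio is not stated), giving 45 in RELAX; a true AE risk of 5% (an assumption). Number with AE data: 45 if all are asked; 0.75 × 45 = 33.75, about 34, under the 25% dropout in the sample size text; 0.5 × 45 = 22.5, taken as 22, if only about half contribute. Those lost are assumed to give no AE data at all.

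Chance of at least one observed case, 1 − 0.95^n:
- n = 45: 0.901
- n = 34: 0.825
- n = 22: 0.676

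One-sided 95% upper bound when no event is seen, 1 − 0.05^(1/n):
- n = 45: 6.4%
- n = 34: 8.4%
- n = 22: 12.7%

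The calculation treats loss as unrelated to having an AE. If loss were more common after an AE, under-recording would be worse; the documents give no figure from which to size that.

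**The case against.** The strongest reply is that diary and PMR are separate tasks. Usual-care subjects keep the same diary with PMR blocked, and payment is for data entered, not for relaxation. A subject who stops PMR because of anxiety is still paid to keep reporting. The paid period spans the whole 8-week schedule, the most intensive practice falls in the first weeks, and the diary is not said to close at day 60. Subjects who later drop out also contribute entries until they leave. All of this stands, and it makes the lower end of the range in the illustration a worst case.

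Other routes could reveal some harms: reasons for non-adherence (Table 2), the PROMIS anxiety screen in REDCap, healthcare-utilization data, and 24- to 48-hour reporting of unanticipated events. These are real but partial. The first has no stated method or timing, the second no stated schedule, the third misses events without a care contact, and the fourth applies only once an event is known. None solicits AEs.

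It can also be said that contact scripts and the treatment manual are not in this document and might contain an AE question. That is possible, so the point is limited to what the plan states.

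A reader might infer that the diary is what drop-outs abandon first, that harms in stoppers are simply missed, or that the reported AE rate will certainly be too low. The documents support none of these. They do not describe the order in which activities stop, and limited follow-through is not the same as giving no AE data.

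**Conclusion.** The point holds as a gap in solicitation. AEs are a listed outcome with one named instrument, and no other step is stated to ask about them. The main weakness is in subjects who stop using the app; the period after day 60 is a lesser one, concerning continued use and later effects. A reader might quote 33% as the share of follow-up with AE capture, but that ignores the match between 60 days and the 8-week intervention and treats the diary as closed when it is not.

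In size, detection of a 5% AE falls from 90% to between 82.5% and 68%, and the zero-event bound rises from 6.4% to between 8.4% and 12.7%. These figures rest on 1:1 allocation, an assumed 5% risk and no AE data from those lost. For a study described as minimal risk this does not threaten the main aims, but it limits what can be said about the tolerability of PMR and about why subjects left. It should be changed.

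**What to change.** Keep the real-time diary. Add a short fixed AE question set, identical in both arms: new or worse anxiety, pain at a previously injured site, intrusive memories, any other event, and whether PMR or the app was stopped because of it. Ask it at each existing contact (1 week; 1, 2, 3 and 6 months), at the call after 3 days without an entry, at withdrawal, and at the existing end-of-study contact of withdrawn subjects who agree. State the AE window as enrolment to 6 months. Report diary-recorded and contact-solicited AEs separately and combined, by arm, with the number of subjects contributing to each.

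In the same amendment, reconcile the Quality Control text, which uses the diary download for safety review, with the confidentiality text, which limits staff access to diary data to checking completeness.

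The cost is a protocol and REDCap form amendment and one to two minutes per contact, with no new visits. Solicited questions will raise the reported AE count somewhat, and contact reports rely on recall of up to three months between months 3 and 6, which is why the diary should stay alongside them.
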